BCS	Breast Cancer Survivor
BMD	Bone Mineral Density
BSI	Bone Strength Index
BW	Body Weight
Ca	Calcium
CaD	Calcium + Vitamin D
CITI	Collaborative Institutional Training Initiative
CCORDA	The College of Public Health and Center for Collaboration on Research Design and Analysis
CLIA	Clinical Laboratory Improvement Amendments
CON	College of Nursing
CRC	Clinical Research Center
CSA	Cross-Sectional Area
CU	Creighton University
D	Vitamin D
DSCM	Data and Safety Monitoring Committee
DXA	Dual Energy Absorptiometry
ELISA	Enzyme-Linked Immunosorbent Assay
ET	Exercise Trainer
FRAX	Fracture Risk Assessment
FSH	Follicle-Stimulating Hormone
FQHC	Federally Qualified Health Center
HSA	Hip Structural Analysis
IA	Iowa
M	Month
N	Number (typically refers to subjects)
NE	Nebraska
NIH	National Institute of Health
NINR	National Institute of Nursing Research
NOCCC	North Omaha Community Care Council
NOF	National Osteoporosis Foundation
NTx	N-terminal Telopeptide

ONJ	Osteonecrosis of the Jaw
ORC	Osteoporosis Research Center
PARQ	Physical Activity Readiness Questionnaire
PHC	People's Health Center
pQTC	Peripheral Quantitative Computed Tomography
PI	Principal Investigator
PTH	Parathyroid Hormone
QCT	Quantitative Computed Tomography
RA	Research Assistant
RCT	Randomized Controlled Trial
RedCAP	Research Electronic Data Capture
Reps	Repetitions
RET	Research Exercise Trainer
RM	Repetition Maximum
RM-ANOVA	Repeated Measures Analysis of Variance
RN	Research Nurse
ROM	Range of Motion
RPE	Rate of Perceived Exertion
RSF	Research Support Fund
SAHP	School of Allied Health Professionals
SOCCC	South Omaha Community Care Council
ST	Strength/Weight Training
Steps	Steps each leg
TNMC	The Nebraska Medical Center
TSH	Thyroid Stimulating Hormone
UL	Upper Limit
UNMC	University of Nebraska Medical Center
US	United States
VCF	Vertebral Compression Fracture
Y	YMCA

PROTOCOL SUMMARY

Title:	Bone Loading Exercises versus Risedronate on Bone Health in Postmenopausal Women
Study moniker:	Heartland Osteoporosis Prevention Study (HOPS)
Précis:	This stratified random study will compare changes in bone strength (bone structure, formation, and bone mineral density) at the hip and spine in women who take 12 months of either: 1) optimal calcium and vitamin D alone; 2) the bisphosphonate "risedronate" with calcium and vitamin D; or 3) a bone-loading exercise program with calcium and vitamin D.
Objectives:	
Our long-term goal is to contribute development of clinical practice guidelines for the promotion of bone health in postmenopausal women with low bone mass, thus reducing the personal and societal burden of osteoporotic-related fractures.
 
Specific Aims:
 
Aim1: To compare Control, Risedronate, and Exercise group subjects on changes in bone structure at the tibia (bone strength index [BSI]: pQCT) and hip (femoral neck and shaft, intertrochanteric) (hip structural analysis: [HSA: DXA]) at baseline, 6, 12 months.
 
Aim2. To compare Control, Risedronate, and Exercise group subjects on changes in BMD at the total hip, femoral neck, and spine (DXA) at baseline, 6, 12 months.
 
Aim3: To compare Control, Risedronate, and Exercise group subjects on changes in bone formation and resorption at baseline, 6, 12 months. (formation: AlkphaseB, resorption: Serum NTx).
 
Aim4: To explore relationships between adherence to exercise (%sessions attended) or adherence to risedronate (% pills taken) and changes in bone structure at the tibia (BSI) and hip (HSA).

Population:	
A total of N = 246 subjects are needed to achieve the proposed objectives. The subjects will be randomized and evenly allocated across three groups. In order to account for a realistic amount of attrition (20%), N = 309 participants will be recruited for this study so that at least N = 246 should be retained if 20% of participants do not complete the study. In order to enroll 309 participants who meet criteria for the study, we are expecting to screen 900 women for eligibility.
 
All subjects must: a) be women who are in their first 5 years of menopause (Menopause will be defined as either not having had a menstrual period in 12 months or having had both ovaries removed. In addition, FSH testing will be conducted on women who are unsure of their menopause status); b) weigh 300 pounds or less; c) not use medications or have diagnoses that

	would interact with the individual's ability to adhere or safely complete any of the study components; d) have a T score between 1 and -2.49 at the femoral neck, total hip, or L1-L4 spine skeletal sites as measured by Dual Energy Absorptiometry (DXA); f) be 19 years of age or older; and g) have their health care providers permission to enroll in the study.
Number of Sites:	
Intervention implementation and data collection will take place at the following sites:
 
 • University of Nebraska Medical Center • The Nebraska Medical Center • Creighton University Medical Center, Osteoporosis Research Center • Omaha, Lincoln, and Council Bluffs-based YMCAs 
Additionally, we will be contacting large organizations in Omaha, such as Mutual of Omaha, as well as community centers, medical facilities, etc. to determine interest in advertising this research study at their facilities. Therefore, information for recruitment purposes will be available to potential subjects at entities which choose to advertise information about the Heartland Osteoporosis Research Study.

Description of Intervention:	
This proposed study has a randomized 3-group (2 treatment groups & 1 control group), repeated measures experimental design. A computer generated code will be used to stratify subjects by exercise at baseline and then randomized to 3 groups (Control: n =103; Risedronate: n =103; Exercise: n =103) with assignments placed in sealed opaque envelopes for sequential use. All subjects will take dosages of calcium citrate supplements sufficient to ensure their total daily calcium (diet+supplements) is ~ 1200 mg daily and vitamin D³ supplements with daily dose to ensure serum levels of vitamin D [25 (OH)D] are between 30 ng/mL and 80 ng/mL(optimal CaD). Subjects randomized to the Risedronate group will take optimal CaD daily and 150mg of oral risedronate once monthly for 12 months but will not participate in the exercise program. Subjects randomized to the Exercise group will take optimal CaD and also participate in 12 months of a bone-loading exercise program three times weekly at a local community-based YMCA (Y). To ensure the bone outcomes were not due to the CaD supplementation, a group taking only optimal CaD will serve as a control. While only women in the exercise group will participate in the structured bone-loading exercise program developed for this study, all women will be encouraged to participate in exercises and will be informed of the benefit of weight bearing and resistance exercises. The primary outcome will be bone structure at the tibia and hip and secondary outcomes are bone mineral density (BMD) and bone turnover. Repeated measures of primary and secondary outcome variables will be conducted at baseline, 6 and 12 months to better understand response to intervention components with a

	maximum difference expected at 12 months. An exercise intervention lasting 12 months or 2 to 3 bone turnover (resorption / formation) cycles is necessary in order to measure the effects of training on bone outcomes.
Study Duration:	Time from subject enrollment to completion of analysis is 4 years and 6 months.
Subject Participation Duration:	Each subject will be asked to participate in the study for a total of 12 months.
Estimated Time to Complete Enrollment:	Study enrollment will begin in Year 1, month 6 and continue through Year 4, month 9.

SCHEMATIC OF STUDY DESIGN:

See [Protocol 1. Timeline for Data Collection](#), for details regarding collection of specific measures

Prior to
Enrollment

Prescreening: Prescreening form and PARQ

Screening:

Eligibility assessed by tests performed in the following order: 1) DXA; 2) laboratory analysis of CBC, serum vitamin D, calcium, creatinine, parathyroid hormone. Analysis of follicle stimulating hormone and/or thyroid stimulating hormone performed if necessary (See Section 7.1); 3) Fracture Risk Assessment; 4) Provider permission for participation

Baseline

Randomize

Optimal Calcium
& vitamin D (CaD)
N=103

Optimal CaD +
Risedronate
N= 103

Optimal CaD +
Exercise
N=103

Perform baseline assessments

3 months

Assessments of subject compliance and evaluation of supplement dose

6 months

Follow-up assessment of baseline outcome measures and safety

12 months

Post-Intervention assessments of outcome measures and safety

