4 STUDY DESIGN

This study has a stratified, randomized 3-group (2 treatment groups & 1 control group), repeated measures experimental design. A computer generated code will be used for randomization to 3 groups (Control: n =103; Risedronate: n =103; Exercise: n =103) with assignments placed in sealed opaque envelopes for sequential use. All subjects will take dosages of calcium citrate supplements sufficient to ensure their total daily calcium (diet+supplements) is ~ 1200 mg daily and vitamin D³ supplements with daily dose to ensure serum levels of vitamin D [25 (OH)D] are between 30 ng/mL and 80 ng/mL(optimal CaD). Subjects randomized to the Risedronate group will take optimal CaD daily and 150mg of oral risedronate once monthly for 12 months but will not participate in the exercise program. Subjects randomized to the Exercise group will take optimal CaD and also participate in 12 months of a bone-loading exercise program three times weekly at a local community-based Y. To ensure the bone outcomes were not due to the CaD supplementation, a group taking only optimal CaD will serve as a control. We believe it would be unethical for women at risk for further bone loss to have restrictions in physical activity for 12 months. Thus, while only women in the exercise group will participate in the structured bone-loading exercise program developed for this study, all women will be encouraged to participate in exercises and will be informed of the benefit of weight bearing and resistance exercises. **The primary outcome will be bone structure at the tibia and hip and secondary outcomes are BMD and bone turnover.** Repeated measures of primary and secondary outcome variables will be conducted at baseline, 6 and 12 months to better understand response to intervention components with a maximum difference expected at 12 months. An exercise intervention lasting 12 months or 2 to 3 bone turnover (resorption / formation) cycles is necessary in order to measure the effects of training on bone outcome

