5.3 Treatment Assignment Procedures

A computer generated code will be used for randomization to 3 groups (Control: n =103; Risedronate: n =103; Exercise: n =103) with assignments placed in sealed opaque envelopes for sequential use.

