Osteoporosis Knowledge Test Revised (*must be 1st questionnaire), *Form 21. Demographic Profile*, *Form 22. FRAX*, *Form 23. Screening Participants Contact Information Form* *_Revised*, *Form 24. Human Activity Profile Test (HAP)* and *Form 25. International Physical Activity Questionnaire (IPAQ)*(see *Protocol 25. Administering Osteo Knowledge Test* ; *Protocol 26. Administering FRAX*; *Protocol 27. Administering HAP Questionnaire*; *Protocol 28. Administering IPAQ*

6. Step 4: Reporting DXA Results

- a. Using the *Form 26. Bone Mineral Density Report*, report DXA results to participant.
 - i. *If DXA results indicate that the participant has either normal bone density, or that they are osteoporotic*, inform participant that they do not qualify for HOPS
 - E. Provide *Form 27. Calcium FAQ*, *Form 28. Vitamin D FAQ*, and *Form 29. Osteoporosis Pamphlet*
 - F. If the screener is osteoporotic, HOPS personnel can refer them to a provider for follow up using the *Protocol 29. Referral for Osteoporotic Screeners*.
 - G. Provide a flyer or two and ask participant to help spread the word about HOPS to friends and family.
 - H. The participant is now finished and may leave.
- b. *If the DXA shows that she has low bone mass (T score between-1 and -2.49), but not yet osteoporosis (T score < -2.5)*, the screening subject will be informed that they qualify for the next stage of screening, which includes a blood draw and blood pressure check.
- c. Confirm that screener wants to proceed with the next stage of screening and complete tasks outlined in #7: Step 5, immediately below.

7. Step 5: Blood Draw, BP, and concluding visit:

- a. *If the screener needs to have their blood drawn at the CRC*:
 - i. Take blood pressure using *Protocol 30. Checking Resting Blood Pressure* as a guide. Record results on Checklist.
 - ii. Discuss an approximate date/time for blood draw so that we know when to expect communication from the CRC.
 - iii. Hand them the following forms: *Form 30. CRC Qualification*, *Form 31. CRC Directions with Map*, *Form 32. Further Questions Contact Sheet* *_Revised* and *Form 29. Osteoporosis Pamphlet*
 - iv. Inform participant that we will contact them once we receive the results of their lab work, and at that point, will send a letter to their provider regarding participation in HOPS (see *Form 33. Provider Permission Letter* *_4*).
 - v. Allow participant to leave.

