6.4.4 Enrollment/Baseline

To print the forms needed for an enrollment visit, see *Packet 3. Enrollment Visit Forms*. All other forms needed for this visit are in RedCap. Checklists for this visit are printed and available at the ORC.

1. Complete process of informed consent to the Main Study (see *Form 34. Main Study Consent*; see *Protocol 39. Main Study Consent Guidelines for Completion*.)
2. Randomization: Open the next envelope (envelope on the “top” of the pile located in desk in HOPS office at ORC) and read treatment group out loud.
3. Select the appropriate checklist (see *Form 35. Enrollment Checklist Exercise*, *Form 36. Enrollment Checklist Control*, *Form 37. Enrollment Checklist Risedronate*)
4. Participant will complete *Form 43. NOF Calcium Intake Estimate_Revised* using paper and pencil (see *Protocol 40. NOF Calcium Intake Calculator*)
5. Walk the participant down to the ORC, where they will complete the PQCT. Leave study Checklist with the participant, so that the ORC personnel can initial that the Pqct has been completed. This scan takes approximately 5 minutes.
6. During pQCT:
 1. Open RedCap complete the ID# assignment using *Protocol 24. RedCap Data Entry* (see also *Packet 4. Control Group_All Enrollment Forms*, *Packet 5. Risedronate Group_All Enrollment Forms*, *Packet 6. Exercise Group_All Enrollment Forms*, if you are using hard copy questionnaires).
 2. Locate appropriate Participant Manual (see *Packet 7. Control Group_Participant Manual*, *Packet 8. Risedronate Group_Participant Manual*, *Packet 9. Exercise Group_Participant Manual*). These are located in the ORC, although personnel will need to print copies of these periodically.

Control Group Protocol:

1. Participant Manual will contain the following:
 - a. *Form 15. One Page Study Summary_3*
 - b. *Form 38. What is Osteoporosis*
 - c. *Form 39. Exercise and Your Bones*
 - d. *Form 40. Instructions for Calcium and Vitamin D*
 - e. *Form 1. Calendar Card Instructions*
 - f. *Form 41. Lexicomp Online Patient Education Cholecalciferol*
 - g. *Form 42. Lexicomp Online Patient Education Calcium Citrate*
2. Participant will complete the *Form 44. Health History Form* in RedCap
3. Research Project coordinator will educate participant on CaD referencing *Form 45. Instructions for Calcium and Vitamin D Usage* and using *Protocol 42. Administering Edu CaD* as a guide.

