10.3 Final Analysis Plan

Aim 1 hypotheses will be tested via RM-ANOVA models. Bone strength index at the tibia and bone mass distribution at the hip, the dependent variables of interest, will be measured at 6-month intervals (0, 6, and 12 months). A significant time*group interaction would indicate that the two groups being compared in each model have significantly different changes in bone structure over 12 months. Huynh-Feldt corrected F-tests will be used in order to account for any possible violation of sphericity. It is hypothesized that the exercise group will have significantly greater improvements than the control or risedronate groups. Up to 20% attrition may be expected over the course of the study, but we expect it

to be less due to the use of cognitive behavioral strategies by Research Project Coordinators (RPC), the Research Exercise Trainer (RET), and ETs to promote exercise adherence and retention in the study. The method of handling missing data is not likely to have an effect with small amounts of missing data. However, If there is a higher than expected attrition rate, a maximum likelihood estimation method (e.g. mixed models) will be used instead of RM-ANOVA in order to utilize all available data and not delete cases in a listwise manner.

Hypothesis 2a compares the groups changes in BMD and will also be analyzed using RM-ANOVA. Hypothesis 2b also involves BMD, but assesses the proportions of preservation of BMD in each group. It is expected that at least 80% of subjects in both the exercise+ and risedronate+ groups will have preserved BMD at the three skeletal sites, and that the control/CaD group will have a significantly lower proportion of participants preserving BMD over 12 months. In order to classify individuals into preserved vs. declined groups, change in BMD over 12 months will be compared to the least significant difference as defined by the Hologic DXA manufacturer for each respective skeletal site. Differences of proportion of preservation across groups will be assessed via chi-square tests, which would indicate if preservation of BMD was significantly different across groups. Aim 3 investigates the changes in bone formation and resorption over 12 months also using repeated-measures ANOVA. Alkphase B and Serum NTx will be measured at baseline, 6, and 12 months.

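### Randomisation is declared stratified by exercise at baseline, but the allocation steps show no stratum and no analysis in section 10.3 carries a term for it (minor impact)

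*Combined protocol and SAP*

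**What the plan says.** The Description of Intervention in the Protocol Summary names the factor: "A computer generated code will be used to stratify subjects by exercise at baseline and then randomized to 3 groups". The précis ("This stratified random study will compare changes in bone strength") and section 4 ("This study has a stratified, randomized 3-group") repeat that the design is stratified but do not name the factor. No categories, cut-off or instrument are given.

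The allocation text is different. Section 5.3 says only "A computer generated code will be used for randomization to 3 groups", with sealed envelopes used in sequence. Section 6.4.4, step 2, has staff open the envelope on top of the "pile located in desk in HOPS office at ORC" and read the group aloud. No stratum look-up is described.

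In section 10.3, Aim 1, H2a and Aim 3 use RM-ANOVA. The test of interest for Aim 1 is the interaction: "A significant time*group interaction would indicate that the two groups being compared in each model" differ in their change over 12 months. A maximum likelihood method such as a mixed model replaces RM-ANOVA if attrition is higher than expected. H2b uses chi-square tests across groups, and Aim 4 uses correlations. No stratum, covariate or baseline-exercise term appears in any of these, or in the power calculation in section 10.2. No reason is given for leaving it out.

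**The concern.** An analysis should normally reflect how the subjects were randomised. If a prognostic factor is balanced by design and then ignored, its variance stays in the error term, so standard errors are too large and tests are conservative. Here the factor is prior exercise in a trial of exercise, so it may plausibly relate to change in bone. At stake are a little power, agreement between the analysis and the design that the report will describe, and a later analyst's freedom to add or omit the factor after seeing the data.

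The plan also leaves open whether stratification was carried out at all. That decides which correction is needed.

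**Working it through.** **Plan's own figure.** Section 10.2 gives f = .10, alpha .05, three time points, correlation .5 and two groups per comparison. The noncentrality is λ = f² × N × m / (1 − ρ). With N = 164, λ = .01 × 164 × 3 / .5 = 9.84 on 2 and 324 degrees of freedom, and power is .805 (N = 162 gives .7998). Then 164 × 1.5 = 246, as stated. Dividing by .8 gives 307.5, so 308, or 309 as a multiple of three.

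**Scale.** If the arms diverge linearly (0, d/2, d), then λ = (82/2) × (d²/2) / .5 = 41d². So d = √(9.84/41) = 0.49 SD at 12 months. With ρ = .5 the SD of a change is √(2 × .5) = 1, so SD units are the same for levels and changes.

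**Which term matters.** A stable level difference between exercisers and non-exercisers is constant within a woman and cancels from the time-by-group test. Only a difference δ in change counts. A stratum main effect alone therefore changes nothing; stratum-by-visit is the term that acts.

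**Assumptions not in the documents.** A share p = .2 to .5 of women exercise at baseline, and exercisers differ by δ = 0.1, 0.25 or 0.5 SD in 12-month change. The last value is an upper corner, as large as the whole treatment target.

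**RM-ANOVA, stratified allocation.** Standard-error inflation with total variance fixed is 1/√(1 − p(1 − p)δ²) − 1. Power is simulated with Huynh-Feldt correction, 82 per arm and 40,000 runs per cell.

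| p | δ | SE too large by | Power without / with stratum-by-visit | Gain (points) |
|---|---|---|---|---|
| .2 | 0.1 | 0.08% | .8030 / .8036 | 0.06 |
| .2 | 0.25 | 0.50% | .8025 / .8043 | 0.18 |
| .2 | 0.5 | 2.06% | .7983 / .8053 | 0.70 |
| .5 | 0.1 | 0.13% | .8036 / .8041 | 0.05 |
| .5 | 0.25 | 0.79% | .8014 / .8042 | 0.28 |
| .5 | 0.5 | 3.28% | .7943 / .8053 | 1.10 |

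Simulation error on one power is √(.8 × .2 / 40,000) = .002, so the smallest gains mean only that the effect is close to zero. With within-stratum variance fixed instead, √(1 + p(1 − p)δ²) − 1 gives at most 3.08%. Type I error is .0494 down to .0454 without the term and .0484 to .0502 with it. If the stratum effect is fully present by 6 months, the p = .5, δ = 0.5 corner gains about 1.6 points.

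**Mixed-model fallback.** With 103 per arm, 15% lost before 6 months and 15% before 12 months, the gain is 0.04, 0.14 and 0.58 points at p = .2, and 0.03, 0.22 and 0.90 at p = .5.

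**No stratification in allocation.** Adding the same terms as ordinary covariates changes power by −0.1, 0.0 and +0.8 points at p = .2, and −0.1, +0.2 and +1.6 at p = .5.

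**H2b, two groups only.** Inputs are 82 per arm and 80% preserved (the H2b target) against an assumed 60%. Chi-square and Cochran-Mantel-Haenszel powers run from .8078 and .8086 (p = .2, exercisers 5 percentage points more likely to preserve BMD) to .8133 and .8253 (p = .5, 20 points). That is a gain of 0.1 to 1.2 points. Type I error runs from .0503 and .0506 to .0442 and .0491. These figures do not describe the three-group test in section 10.3.

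**The case against.** The strongest reply is that this hardly matters. Short of the extreme corner, the gain in the primary model is 0.3 points or less, N = 246 stands and no conclusion is endangered. That is right, and it sets the severity.

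The second reply is that the premise is unconfirmed. Sections 5.3 and 6.4.4 describe no stratum; if none was applied, the conservatism argument falls away and covariate adjustment is optional. That also stands, so the fix branches. It does not remove the point, because on either reading some text has to change.

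A reader might infer more than the documents support, in three ways:

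- **That the tests are biased or too liberal.** Omitting a balanced factor makes them conservative, if anything.
- **That the power loss is serious.** Letting the stratum explain 2% to 20% of the variance in change gives a loss of about 1 to 7 points. With two equal strata R² = δ²/4, so R² of .10 and .20 mean δ of 0.63 and 0.89 SD, both above the 0.49 SD treatment target. That calculation also places an equal stratum effect on the curvature over visits. No figure in the documents supports such effects, and all arms are encouraged to exercise, which may narrow them.
- **That stratification was not done.** The allocation steps read most naturally as a single pile but do not exclude one pile per stratum. The operational protocols and forms are visible by title only.

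**Conclusion.** The inconsistency is certain from the text: a stratification factor is declared, is left undefined, is absent from the described allocation steps and is used in no analysis. Its consequence is small. If allocation was stratified, the planned tests lose about 0 to 1 power point for assumed stratum effects of 0.1 to 0.5 SD in 12-month change (about 1.6 in the corner where the whole effect appears by 6 months). They lose nothing if baseline exercise does not predict change. There is no bias and no type I error inflation. If allocation was not stratified, nothing was omitted from the analysis and the design label is what needs correcting. The exerciser share, the stratum effects and the 60% preservation rate are assumptions. Severity is low; the change is worth making because it costs almost nothing.

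**What to change.** Reconcile the Protocol Summary, précis and section 4 with sections 5.3 and 6.4.4, and state in one sentence in section 10.3 which baseline-exercise stratum was used, if any.

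- **If allocation was stratified:** add stratum and stratum-by-visit, as additive terms, to the Aim 1 to 3 RM-ANOVA models and to the mixed-model fallback. For H2b, replace the chi-square with a Cochran-Mantel-Haenszel test stratified by the factor: the general-association form for the three-group comparison, and the two-group form for any pairwise comparison.
- **If it was not:** remove the word stratified from the précis, the Description of Intervention and section 4. Baseline exercise may then enter as an ordinary covariate with its visit interaction, and should not be called a stratum. Name one questionnaire and one scale, fixed before outcome data are examined by group. A deadline tied to unblinding would not work, because the group is read aloud at enrolment and section 6.1 blinds only the assessors. The expected power change is about −0.1 to +1.6 points.

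The cost is a few sentences. The Human Activity Profile and the International Physical Activity Questionnaire are already completed at screening (section 6.4.2), before randomisation, so no new data, visits or subjects are needed. The allocation sequence and sample size stay as they are.
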